#### **7.4.2. Overall Survival (OS)**

Overall survival is defined as the time from the date of randomization to the date of death due to any cause, censored at the last date known alive on or prior to the data cutoff date. Patients who had PD and started new anticancer therapy will continue to be followed for the OS assessment.

#### **7.4.3. Disease Control Rate (DCR)**

Disease control rate is the proportion of patients who achieve overall tumor response (confirmed CR or PR) or SD as assessed by RECIST 1.1 at least 16 (-1 week tumor assessment window) weeks from randomization.

[figure not shown]
#### **7.4.4. Objective Response Rate (ORR)**

Objective response rate is defined as the proportion of patients demonstrating an objective response during the study. Objective response includes CR and PR as defined in the RECIST 1.1 criteria and must be subsequently confirmed at least 4 weeks later.

[figure not shown]
#### **7.4.5. Duration of Response (DOR)**

Duration of response is measured from the time at which measurement criteria are first met for CR or PR (whichever status is recorded first) until the first date of PD is objectively documented or death. It is censored at the last valid tumor assessment if PD or death has not been documented.

[figure not shown]

### **7.5. Efficacy Analysis Methods**

#### **7.5.1. Primary Analysis of PFS**

[figure not shown]

[figure not shown]
#### **7.5.2. Sensitivity Analyses of PFS**

### **7.5.3. Secondary Efficacy Endpoints Analyses**

## **7.6. Safety Analysis**

### **7.6.1. Overview of Safety Analysis Methods**

[figure not shown]
All safety analysis will be performed for all patients in the Safety population. The following assessments will be used:

- Adverse events (AEs)
- Medical history
- Physical examination findings
- Vital sign measurements
- Laboratory assessments
- ECOG performance status
- ECG
- Liver Function Tests results

All safety endpoints will be summarized by treatment group and visit when appropriate.

### **7.6.2. Extent of Exposure**

Extent of exposure to each investigational product will be summarized by total dose, number of cycles, treatment duration, dose intensity, relative dose intensity, number of missed doses, number of dose delays and number of dose reductions.

### **7.6.3. Concomitant Medications**

Concomitant medications will be defined as medications documented on the Concomitant Medications CRF. Concomitant medications will be coded using the World Health Organization Drug Reference List (WHODrug) dictionary 2021 version and summarized in a table and a data listing.

### **7.6.4. Adverse Events, Serious Adverse Events, and Deaths**

All AEs and SAEs will be reported until 30 days after the last dose of investigational product(s) and will be followed until resolution or until condition stabilizes. AEs and SAEs will be coded using the Medical Dictionary for Regulatory Activities (MedDRA) 24.1 and graded by the Investigator according to the NCI CTCAE v5.0 or later.

Summaries of adverse event will, in general, focus on TEAEs which is defined as adverse event that occurs or worsens on or after first dose of investigational product and up to 30 days after the last dose. Missing data for safety endpoints will not be imputed. If dates are missing or incomplete for adverse event therefore TEAE status cannot be determined, then this AE will be included as an TEAE in the safety analysis.

Subject incidence of the following events will be tabulated in two formats: 1) system organ class (SOC), preferred term (PT), and grade by treatment group; 2) PT only and by treatment group.

- All TEAEs
- SAEs
- Treatment-related TEAEs
- Treatment-related SAEs
- Grade 3 or 4 TEAEs
- TEAE leading to treatment discontinuation, dose reduction, dose interruption
- TEAEs with an incidence >10%
- TEAEs with at least a 5% difference in incidence rates between treatment groups

Listings of TEAEs, TEAEs leading to IP discontinuation, TEAEs related to study treatment, and SAEs will be provided. Listings will be sorted by treatment, patient ID and study day; SAEs will be flagged. All AE listings will include treatment arm, patient ID, study day, SOC, PT, reported term, dose, Cycle/day, AE onset date, AE end date, outcome, duration, relationship to drug, action taken, and severity.

The incidence of death will be summarized by cause of death, treatment arm, and on-study status at time of death (within 30 days of last dose vs. more than 30 days after last dose). Patient death listings will include all death data available including date of death, cause of death and any AEs resulting in death.

AE of special interest may be identified and summarized.

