### **8.2.3 Adverse Event Severity**

AEs will be reported at the highest experienced severity. AE severity will be graded according to NCI CTCAE version 5.0. A copy of the document will be provided to investigational sites and an electronic version is available at:

[https://ctep.cancer.gov/protocolDevelopment/electronic\\_applications/docs/CTCAE\\_v5\\_Quick\\_Reference\\_8.5x11.pdf](https://ctep.cancer.gov/protocolDevelopment/electronic_applications/docs/CTCAE_v5_Quick_Reference_8.5x11.pdf)

The terms “severe” and “serious” are not synonymous. Severity refers to the intensity of an adverse event (e.g., rated as mild, moderate, or severe, or according to the NCI CTCAE); the event itself may be of relatively minor medical significance (e.g., severe headache without any further findings).

Events not listed in NCI CTCAE will be graded according to the criteria described in [Table 133](#).

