**Table 13: Severity Grading Guideline for Adverse Events Not Listed in NCI CTCAE**

Adverse Events Not Listed in NCI CTCAE Version 5.0	
Grade	Description
1	

• Mild

• Asymptomatic or mild symptoms

• Clinical or diagnostic observations only

• Intervention not indicated

2	

• Moderate

• Minimal, local or noninvasive intervention indicated

• Limiting age-appropriate instrumental activities of daily livinga

3	

• Severe or medically significant but not immediately life-threatening

• Hospitalization or prolongation of hospitalization indicated

• Disabling

• Limiting self-care activities of daily livingb

4	

• Life-threatening consequences

• Urgent intervention indicated

5	

• Death related to adverse event

NCI CTCAE = National Cancer Institute Common Terminology Criteria for Adverse Events

a Instrumental activities of daily living refer to preparing meals, shopping for groceries or clothes, using the telephone, managing money, etc.

b Self-care activities of daily living refer to bathing, dressing, and undressing, feeding self, using the toilet, taking medications, and not bedridden.

Note: A semicolon indicates “or” within the description of the grade.

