## **LIST OF PLANNED TABLES, FIGURES, AND LISTINGS**

### **List of Planned Tables**

Category	Title
Disposition	Summary of Randomization
	Summary of Analysis Population
	Summary of Subject Disposition
	Summary of Protocol Deviations
	Summary of Follow-up Time
Demography and Baseline Characteristics	Summary of Demographics
	Summary of Baseline Characteristics
Medical History	Summary of Medical History
Cancer History	Summary of Prior Cancer History
	Summary of Prior Anticancer Medications
	Summary of Prior Anticancer Radiotherapy
	Summary of Prior Anticancer Surgical Therapy
	Summary of Biomarkers
Concomitant Medications	Summary of Concomitant Medications
	Summary of Concomitant Surgery
Study Medication	Summary of Treatment Exposure
	Summary of Treatment Dose Reduction
	Summary of Treatment Dose Hold
Efficacy	Summary of Progression-Free Survival by Central Review
	Summary of Progression-Free Survival by Investigator
	Summary of PFS in Subgroups
	Summary of Objective Response Rate
	Summary of Duration of Response
	Summary of Disease Control Rate
	Summary of Overall Survival
	Summary of Overall Survival in Subgroups
	Concordance of Central PFS and Local PFS

Category	Title
	Summary of Subsequent Anti-cancer Treatment
Health Outcomes	Summary of EORTC QLQ-C30 Observed Results and Change from Baseline
	Summary of EORTC QLQ-C30 Mixed Model Between Treatment Comparison
	Summary of Time to EORTC QLQ-C30 Deterioration
Safety	Summary of Overall Safety
	Incidence of TEAE by Preferred Term
	Incidence of TEAE by System Organ Class, Preferred Term, and Grade
	Incidence of Serious Adverse Events by Preferred Term
	Incidence of Serious Adverse Events by System Organ Class, Preferred Term, and Grade
	Incidence of TEAE Related to Study Treatment
	Incidence of TEAE Leading to Study Discontinuation
	Incidence of TEAE Leading to Study Drug Reduction
	Incidence of TEAE Leading to Study Drug Hold
	Incidence of Grade 3 or 4 TEAE by System Organ Class, and Preferred Term
	Summary of TEAE with Incidence $\geq 10\%$ by Preferred Term
	Summary of Death
	Summary of TEAE of Special Interest
Laboratory	Mean and Mean Change from Baseline in Numeric Laboratory Data: Hematology/ Clinical Chemistry
	Shift from Baseline in Laboratory Data: Hematology/ Clinical Chemistry
Vital Signs	Mean and Mean Change from Baseline in of Vital Signs Data
	Frequency Table of Potentially Clinically Significant Vital Signs Data
Physical Exam	Summary of Physical Examination

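### The SAP's only adverse event table selected by severity stops at Grade 4, so an event that becomes fatal lowers the count in that table

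*SAP*

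**What the plan says.** Among the event sets to be tabulated by subject incidence, SAP 7.6.4 names "Grade 3 or 4 TEAEs". It is the only set in that list chosen by grade. The List of Planned Tables carries the same limit: "Incidence of Grade 3 or 4 TEAE by System Organ Class, and Preferred Term".

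Three other statements determine what the limit does:

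- SAP 7.6.4 has events "graded by the Investigator according to the NCI CTCAE v5.0 or later".
- Protocol 8.2.3 says "AEs will be reported at the highest experienced severity".
- Protocol Table 13, for events not listed in CTCAE, defines Grade 5 as "Death related to adverse event". Table 14, for infusion-related reactions and adapted from CTCAE v5.0, also makes Grade 5 death.

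The SAP plans other displays that keep Grade 5. The first of the two formats in 7.6.4, "1) system organ class (SOC), preferred term (PT), and grade by treatment group", applies to all TEAEs, to serious adverse events (SAEs) and to the treatment-related subsets of both. The List of Planned Tables includes "Incidence of Serious Adverse Events by System Organ Class, Preferred Term, and Grade". For deaths, SAP 7.6.4 states: "The incidence of death will be summarized by cause of death, treatment arm, and on-study status at time of death". The death listing is to show any adverse events that led to death.

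**The concern.** A table of severe events should not improve when outcomes get worse. Under these rules, a Grade 4 event that the patient survives is counted, and the same event ending in death is not. If one arm has more fatal adverse events than the other, its rate in this table is understated relative to the other arm, and the order of the arms can reverse.

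The events lost carry particular weight for a safety comparison. Protocol 8.1.1.1 and 8.5 generally keep deaths from progression out of adverse event reporting, except where the investigator considers them accelerated, atypical or drug-related. The Grade 5 events that remain should therefore include the deaths in which the drug is suspected. Protocol 3.2 makes the safety profile of milademetan against trabectedin a secondary objective.

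**Working it through.** The plan states no figure to reproduce here. The check is whether the passages combine as described, followed by simple proportions.

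**Logic**

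1. The table includes Grades 3 and 4 (SAP 7.6.4 and List of Planned Tables).
2. Each event carries its worst grade (Protocol 8.2.3), so a Grade 4 event that becomes fatal is recorded as Grade 5.
3. Grade 5 is outside the table, so the patient is lost from the row of the term that became fatal.
4. The table counts patients. In any overall row, a patient with another Grade 3 or 4 TEAE is still counted. A patient with no other such event is not.

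**Inputs**

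- About 160 patients randomised 1:1 (SAP 3.1), so 160 / 2 = 80 per arm. The exact denominator is the Safety Population, meaning patients who received at least one dose (SAP 5.2), so 80 is an approximation.
- Numbers of Grade 3 or higher and fatal events are not in the documents. The counts below are assumptions chosen for illustration.

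**Loss per patient**

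Each patient whose only Grade 3 or higher TEAE is fatal lowers the arm's rate by 1 / 80 = 1.25 points.

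**Equal Grade 3 or higher incidence in both arms, with k more such patients in arm B than in arm A**

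Apparent advantage to arm B = k / 80.

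| k | Apparent advantage to arm B |
|---|---|
| 1 | 1.25 points |
| 2 | 2.5 points |
| 4 | 5.0 points |
| 6 | 7.5 points |
| 8 | 10.0 points |

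The gap does not depend on the common Grade 3 or higher count. It is the same at 30, 40 or 50 of 80.

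**Fatal events in both arms**

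Assume arm A has 40 patients with worst grade 3 or 4 and 2 whose only Grade 3 or higher event was fatal. Assume 37 and 6 in arm B.

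- Table as planned: 40 / 80 = 50.0% against 37 / 80 = 46.25%. Arm B looks 3.75 points better.
- Grade 3 or higher: 42 / 80 = 52.5% against 43 / 80 = 53.75%. Arm B is 1.25 points worse.

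The order reverses, although both arms have fatal events.

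**The case against.** The strongest reply is that fatal events are not lost from the report. Death is a seriousness criterion (Protocol 8.1.1.2), so a fatal adverse event is an SAE, and the Grade 5 rows of the SAE table show it by preferred term and arm. The all-TEAE table and the treatment-related tabulations by grade show it too. Deaths are also summarised by cause and arm and listed with any adverse events that caused them. Showing non-fatal severe events apart from fatal ones is a defensible display choice when the fatal ones appear elsewhere. All of this stands, and it limits the point to one table.

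Four stronger readings are tempting, and the documents do not support them:

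- *Fatal events are hidden, or the arm with more of them looks safer overall.* The other displays rule this out. The arm looks better only in this table read alone.
- *The table is the main safety comparison.* The SAP gives it no special rank and attaches no test to it.
- *A 5-point shift crosses a threshold in the SAP.* The 5% difference in 7.6.4 selects TEAEs of any grade for display. It is not a criterion for severe toxicity.
- *No planned output isolates fatal TEAEs.* The visible lists name no dedicated table. However, the rows of the overall safety summary are not shown, and parts of the safety text in both documents are unavailable, so absence cannot be asserted.

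What survives is that a reader who wants Grade 3 or higher incidence must rebuild it from several tables. Adding Grade 5 counts to Grade 3 or 4 counts can count a patient twice if that patient had both.

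**Conclusion.** The point holds as a one-directional distortion of a single table. A fatal outcome can only lower the count there. The size is about 1.25 points per patient whose only Grade 3 or higher TEAE was fatal, so about 1.25 to 10 points for an assumed excess of 1 to 8 such patients in one arm. That range rests on about 80 treated patients per arm and on assumed counts. If fatal adverse events are few, balanced between arms, or occur in patients who also had a Grade 3 or 4 TEAE, the overall rate hardly moves and the loss shows mainly in the preferred-term rows.

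The primary PFS analysis, the analysis populations and data collection are unaffected. This is a reporting correction worth making before results are seen, because choosing the definition afterwards would be open to question.

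**What to change.** In SAP 7.6.4 and in the matching entry of the List of Planned Tables, redefine the set as Grade 3 or higher TEAEs (Grades 3, 4 and 5). Alternatively, keep the Grade 3 or 4 table and show two further columns beside it: Grade 5, and the combined Grade 3 to 5 incidence with each patient counted once.

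The cost is a wording change in two places of the SAP and one program filter. The grade of each event is already recorded, so no new data are needed.

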## **4. STUDY DESIGN**

### **4.1 Study Design Overview**

This is a randomized, multicenter, open-label, Phase 3 registration study designed to evaluate the safety and efficacy of milademetan compared to trabectedin in patients with unresectable (i.e., where resection is deemed to cause unacceptable morbidity or mortality) or metastatic DD liposarcoma that progressed on 1 or more prior systemic therapies, including at least 1 anthracycline-based therapy. Trabectedin is the chosen active control treatment because it has been approved as a second-line therapy by the US FDA for patients with liposarcoma or leiomyosarcoma who received a prior anthracycline-containing regimen. Trabectedin was approved for liposarcoma based on improved PFS. In the current study, the primary objective is to compare PFS, as determined by BICR, between patients receiving milademetan versus trabectedin.

An independent data monitoring committee (IDMC) will review unblinded safety data during the course of the study and make recommendations to the Sponsor as applicable and outlined in the IDMC charter.

[figure not shown]
Approximately 160 patients will be randomly assigned in a 1:1 ratio to receive milademetan or trabectedin. Randomization will be stratified based on Eastern Cooperative Oncology Group

(ECOG) performance status (0 or 1) and number of prior therapies ( $\leq 2$  or  $> 2$ ) for the patient's liposarcoma.

Patients will receive study drug (i.e., milademetan or trabectedin) until reaching unequivocal disease progression (per Response Evaluation Criteria in Solid Tumors [RECIST] version 1.1) as determined by the Investigator, experiencing unmanageable toxicity, or until other treatment discontinuation criteria are met. Patients may be treated beyond tumor progression if they are experiencing clinical benefit based on the assessment of the Investigator in discussion with the Medical Monitor. All patients will be followed for documentation of disease progression and survival information (i.e., date and cause of death) and subsequent treatment information (i.e., date/duration of treatment, response, and subsequent disease progression). Long-term follow-up will continue every 12 weeks ( $\pm 7$  days) until the endpoint of death, the patient is lost to follow-up, or for 24 months following the first dose of study drug of the last patient enrolled, whichever comes first.

The study design is illustrated in [Figure 5](#).

[figure not shown]

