### **11.3 Duration of the Study**

The total study duration is estimated to be 4 years, including approximately 12 months for accrual of patients, up to 12 months of treatment for each patient, and up to 24 months of long-term follow-up following the first dose of study drug of the last patient enrolled. The end of the study is defined as the last patient visit or contact, including telephone contacts, for collection of any study-related data.

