## **1. INTRODUCTION**

This statistical analysis plan (SAP) outlines the statistical methods to be implemented for study RAIN-3201 entitled “A Randomized Multicenter Phase 3 Study of Milademetan Versus Trabectedin in Patients with Dedifferentiated Liposarcoma”. The purpose of the SAP is to ensure the credibility of the study findings by pre-specifying the statistical approaches to the analysis of study data prior to the primary analysis. Results of the planned analyses in this SAP will become the basis of the clinical study report (CSR) for this protocol.

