## **6. INTERIM ANALYSIS AND DATA MONITORING**

[figure not shown]
No interim PFS analysis is planned. One OS interim analysis is planned at the time of the primary PFS analysis. The final OS analysis will be performed at the end of the study when all patients complete the 24-month long-term follow-up.

An independent data monitoring committee (IDMC) will review accumulating data periodically throughout the study and to make recommendations to the Sponsor regarding the conduct of the study in order to safeguard the interests of trial participants while preserving the integrity and credibility of the study. The Sponsor will implement guidelines to provide internal access of unblinded data on a strictly as required basis for the purpose of data capture, cleaning and analysis of this study. An independent biostatistician external to the Sponsor will prepare analyses for the IDMC.

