## **7. STATISTICAL METHODS OF ANALYSIS**

### **7.1. General Principles and Reporting Conventions**

The primary goal of the statistical analysis of the study is to demonstrate whether there is an increase in PFS in subjects treated with milademetan versus trabectedin in ITT population. The timing of the primary analyses of PFS will be event-driven based on corresponding pre-specified goals for the target number of 105 PFS events in the ITT population. The primary analysis of PFS and other RECIST endpoints will be according to BICR. Sensitivity analyses using investigator assessed tumor response or disease progression will be performed, using similar analysis sets of local review.

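### The visible safety plan (SAP 7.6.4) compares arms only by crude adverse-event incidence, although the design expects longer treatment on milademetan

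*SAP*

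**What the plan says.** SAP 7.6.4 sets the measure: "Subject incidence of the following events will be tabulated in two formats", by system organ class, preferred term and grade, and by preferred term alone. A treatment-emergent event is one that starts or worsens between first dose and 30 days after last dose. One of the tabulated categories is "TEAEs with at least a 5% difference in incidence rates between treatment groups".

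The List of Planned Tables carries the matching crude entries, for example "Incidence of TEAE by System Organ Class, Preferred Term, and Grade". It has no entry for the 5% list and none for an exposure-adjusted, time-to-event or fixed-window AE table.

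Treatment duration is summarised separately (SAP 7.6.2), and the AE listings show study day and onset date. Under Protocol 4.5, drug is given until progression or unacceptable toxicity.

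The visible text does not say when safety data are cut. SAP 7.1 ties the PFS analysis to "pre-specified goals for the target number of 105 PFS events in the ITT population". SAP 6 says "The final OS analysis will be performed at the end of the study when all patients complete the 24-month long-term follow-up". SAP 1 says "Results of the planned analyses in this SAP will become the basis of the clinical study report", without naming a cutoff for safety.

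**The concern.** Crude incidence rises with time at risk. A trial designed to double median PFS, with treatment to progression, should expect patients to stay longer on milademetan. An event with the same monthly risk in both arms would then be seen in more milademetan patients, and a real excess on trabectedin would look smaller. The duration summary shows that exposure differs, but no planned table shows how much of any event's difference comes from it.

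At stake is a stated comparative aim. Protocol 3.2 frames the safety objective as milademetan against trabectedin, although the Synopsis and SAP 2.2 name milademetan only. The PFS and OS comparisons and their error rates are unaffected.

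**Working it through.** The plan gives no AE rate, no time on drug by arm and no safety cutoff, so it has no figure of its own to reproduce. The check asks what crude incidence would show if the true risks were equal.

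**Inputs from the documents**
- Median PFS at most 3 months on trabectedin (3 used) and 6 on milademetan (Protocol Synopsis).
- About 160 patients, 1:1, so 80 per arm.
- 105 PFS events (SAP 7.1).
- Accrual and treatment: "approximately 12 months for accrual of patients, up to 12 months of treatment for each patient" (Protocol 11.3).
- Follow-up: "for 24 months following the first dose of study drug of the last patient enrolled" (Protocol 4.1), so 12 + 24 = month 36.
- A 30-day tail after last dose, taken as 1 month.

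**Assumptions**
- Time on drug is exponential with the PFS medians, and accrual is uniform.
- Event hazards h are constant at 0.02, 0.05 or 0.10 per month.
- The 5% means absolute points, which is 4 of 80 patients.

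**Step 1: date of 105 events.** With μ = ln2/median (0.2310 and 0.1155 per month) and entry time s uniform on 0–12, solve 80·mean[1 − exp(−0.2310(t − s))] + 80·mean[1 − exp(−0.1155(t − s))] = 105. This gives t = 13.56 months (61.1 + 43.9 events).

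**Step 2: time at risk.** The chance of still being at risk at time x is S(x) = 1 for x < 1 and exp(−μ(x − 1)) after. At month 13.56 the mean is 4.0 months on trabectedin and 5.3 on milademetan, a ratio of 1.30.

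**Step 3: crude incidence with equal hazards.** Incidence = mean over s of ∫₀^(t−s) h·e^(−hx)·S(x) dx. The listing chance is exact binomial with 80 per arm and an observed difference of at least 5 points.

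| Cutoff | Difference, milademetan minus trabectedin (points), h = 0.02 / 0.05 / 0.10 | Chance listed as higher on milademetan |
|---|---|---|
| 105 events | 2.2 / 4.6 / 7.0 | 31 / 51 / 63% |
| Month 24 or 36, treatment capped at 12 months | 4.2 / 8.4 / 12.0 | 48 / 72 / 84% |
| Month 24, no cap | 5.2 / 10.0 / 13.4 | 56 / 79 / 88% |
| Month 36, no cap | 6.3 / 11.5 / 14.5 | 64 / 85 / 90% |

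At 105 events the incidences are 7.6 vs 9.8%, 17.7 vs 22.2% and 31.2 vs 38.2%. If both arms had trabectedin's exposure, the listing chances would be 15, 23 and 28%. The expected difference reaches 5 points only for trabectedin incidences of about 20–83% at 105 events, and 8–88% at month 36 without a cap.

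**Step 4: a true 1.5-fold hazard on trabectedin.**
- At 105 events it shows as 11.2 vs 9.8%, 24.9 vs 22.2% and 41.9 vs 38.2% (trabectedin first). That is 1.3, 2.6 and 3.7 points, against 3.5, 7.2 and 10.6 if both arms had trabectedin's exposure.
- The chance of listing it as higher on trabectedin is 26, 40 and 47%, against 42, 67 and 80%.
- At month 24 without a cap the order reverses (13.9 vs 14.8%, 29.8 vs 31.6%, 47.7 vs 50.1%). With the 12-month cap the arms look about equal (13.6 vs 13.6%, 29.4 vs 29.6%, 47.5 vs 48.3%).

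**Step 5: the same hazards over a 12-week window** (2.76 months, end of the at-risk period as a competing event).
- Equal hazards give 4.8 vs 5.0%, 11.5 vs 12.1% and 21.6 vs 22.8%.
- The 1.5-fold excess shows as 7.1 vs 5.0%, 16.7 vs 12.1% and 30.5 vs 22.8%.
- At the 105-event cutoff, 90% of patients are at least 12 weeks past randomization.

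**Step 6: sensitivity at the 105-event cutoff** (equal hazards; points for the three values of h).

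| Change | Difference |
|---|---|
| Milademetan median 4.5 months (cutoff month 12.8) | 1.1 / 2.4 / 3.8 |
| Extra stopping of 0.05/month, milademetan only | 1.1 / 2.3 / 3.5 |
| Extra stopping of 0.10/month, milademetan only | 0.2 / 0.5 / 0.7 |
| Extra stopping of 0.05/month, both arms | 1.7 / 3.7 / 5.6 |
| Extra stopping of 0.05/month, trabectedin only | 2.8 / 5.9 / 9.1 |

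Extra milademetan stopping of ln2/3 − ln2/6 = 0.116 per month cancels the effect at any cutoff. Risk confined to the first 1, 2 or 3 months gives at most 0, 1.1 or 2.9 points.

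**The case against.** - **Hidden text.** Protocol section 9 and SAP 7.6.8 cannot be read, and either could hold a safety cutoff or an exposure adjustment. SAP 7.4.2 refers to a data cutoff date for OS as if it were defined. This stands as a limit: the gap is shown only for the visible text.
- **A legitimate analysis.** Crude incidence to 30 days after last dose is a coherent description, and nothing in the plan contradicts it. That stands too, so this is an improvement and not an error.
- **Partly covered.** Duration is summarised, listings carry dates, and SAP 7.6.1 allows summaries by visit where appropriate. A reader can see that exposure differs, but none of this adjusts an AE comparison.
- **A noisy list.** The 5% list is descriptive and works both ways. With equal exposure, 15, 23 and 28% of events would be listed in each direction, so 30–56% in total. The list supports little by itself, but unequal exposure adds a directional push to that noise.
- **The fix helps unevenly.** Over 12 weeks, the 1.5-fold excess would be listed as higher on trabectedin about 26, 51 and 68% of the time, against 26, 40 and 47% with the crude table. At the lowest hazard detection does not improve. False listing on milademetan does fall, to about 11, 23 and 31%.
- **Size rests on assumptions.** Treatment stops on Investigator-assessed progression, toxicity or other criteria and may continue past progression, so PFS by central review is only a proxy. This is the strongest point. It makes the size, and even the direction, uncertain; it does not make crude incidence a fair comparison when exposure differs.

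**Conclusion.** The concern holds as an inexpensive improvement. In the visible plan, adverse events are compared between arms only by crude incidence over a window that lengthens with treatment.

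If time on drug follows the design's PFS assumptions and risk is steady, common events tilt towards milademetan. The tilt is modest at the 105-event cutoff and about 1.7 to 1.9 times as large at a later cutoff with treatment capped at 12 months (4.2/2.2 and 12.0/7.0). At 105 events a true 1.5-fold trabectedin excess keeps its direction but loses about two thirds of its size (1.3/3.5 = 0.37; 3.7/10.6 = 0.35). It disappears or reverses only with longer follow-up. Confidence is medium, because the documents give neither time on drug by arm nor a safety cutoff.

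**What to change.** Keep the crude tables and the 5% list. In SAP 7.6.4:

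1. State the safety data cutoff, and say that 5% means absolute percentage points.
2. For TEAEs, SAEs and Grade 3 or higher TEAEs, add cumulative incidence over a common early window, for example the first 12 weeks, accounting for end of the at-risk period and for data cutoff. Apply the 5% difference to this incidence as well.
3. Add exposure-adjusted first-event rates per 100 patient-months as a supplement only. Used alone they understate early toxicity in the arm treated longer. An identical 20% risk confined to month 1 gives 100·p/[p/h + (1 − p)·E], with p = 0.20, h = −ln 0.8 and E the mean later time at risk. That is 6.0 (trabectedin) vs 4.6 (milademetan) at the 105-event cutoff (E = 3.04 and 4.27 months), and 4.6 vs 2.6 with complete follow-up (E = 4.33 and 8.66).
4. Reconcile the AE window, since these tables need one definition of time at risk. Protocol 8.2.1 ends collection at new anticancer therapy if that comes before 30 days; SAP 7.6.4 uses 30 days without that condition.
5. Add the new tables and the 5% list to the List of Planned Tables.

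The cost is SAP wording and a few tables from data already collected. A fixed window misses late events, and the rates assume a roughly constant hazard, which is why the crude tables should stay.
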